		6.2.4	Reference non-inferiority margin in section 12 and rationale for differences in events per hour	Clarification between power and non-inferiority margin calculations
		12.	Further explanation on non-inferiority margin and clinical justification for the margin	To make statistical analysis more clear
4.0	06.June.2016	Various	iVAPS to VAPS	To better define the objective of comparing AutoEPAP to manual EPAP; these modes will be utilized within the iVAPS mode on the Astral study device
		4.1	Updated study device with current FDA clearance status and K number Updated language referencing previous clinical data	To reflect current FDA clearance status on study device Provide clarity to the details of this research
		4.2	Update to intended use language	Ensure protocol is consistent with currently cleared IFU language

		5.2	Update patient description to be “respiratory failure”	Update language of patient population to be more clinically accurate
		6.2.5	Update to I#6 wording	Clarify purpose of this criteria
		6.2.6	Removal of “dependent” from Exclusion criteria	Current cleared IFU for study device does not exclude this type of patient
		7.4	Update to training process	Reflect current protocol training procedures
		9.1	Update to appropriate data transfer method	Previous version was inaccurate with old SD card method
		9.3	Summary of Visit 3 added	Clarification of visit 3 procedures
		10.	Update to study timeline and total enrollment	Change in IEC of protocol dictates an increase of total sample size, and consequently, increase in study timeline
		14.3.1	Update to NSR justification	Provide current FDA clearance for study device

Table of Contents

1. RESPONSIBILITIES AND ADDRESSES	7
2. ABBREVIATIONS AND DEFINITIONS	8
3. PROTOCOL SUMMARY	10
4. INTRODUCTION	12
4.1. BACKGROUND INFORMATION	12
4.2. INTENDED USE	14
5. STUDY OBJECTIVES.....	14
5.1. PRIMARY OBJECTIVE.....	14
5.2. SECONDARY OBJECTIVES.....	14
6. STUDY DESIGN.....	15
6.1. ENROLLMENT	15
6.2. SELECTION OF SUBJECTS	15
6.2.1. INFORMED CONSENT	15
6.2.2. STUDY POPULATION AND RANDOMIZATION.....	15
6.2.3. NUMBER OF SUBJECTS	15
6.2.4. SAMPLE SIZE JUSTIFICATION.....	15
6.2.5. SUBJECT INCLUSION CRITERIA	16
6.2.6. SUBJECT EXCLUSION CRITERIA	16
7. STUDY DEVICES	17
7.1. ASTRAL DEVICE	17
7.2. DEVICE ACCOUNTABILITY.....	17
7.3. LABELING.....	17
7.4. PACKAGING	17
7.5. INSTRUCTION FOR USE.....	17
7.6. REQUIRED TRAINING	18
8. THERAPY	18
8.1. TREATMENT WITH ASTRAL DEVICE	18
8.2. SET UP OF ASTRAL DEVICE.....	18

2. ABBREVIATIONS AND DEFINITIONS

ITEM	DEFINITION
AASM 2007	American Academy of Sleep Medicine 2007 guidelines
ABGs	Arterial blood gases
AHI	Apnea Hypopnea Index
COPD	Chronic Obstructive Pulmonary Disease
CPAP	Continuous positive airway pressure
CRF	Case report form
DSBM	Data & Safety Monitoring Board
EEG	Electroencephalography
EFL	Expiratory flow limitation
EPAP	Expiratory positive airway pressure
EPR	Expiratory Pressure Relief (ResMed comfort setting)
HREC	Human Research Ethics Committee
iBR	Intelligent Back-Up Rate
ICF	Informed Consent Form
IRB	Institutional Review Board
iVAPS	Intelligent Volume Assured Pressure Support
Astral	The name given to the clinical trial device
LSLV	Last subject, last visit
NIPPV	Non-invasive positive pressure ventilation
NMD	Neuromuscular Disease
NSR	Non-Significant Risk
ODI	Oxygen desaturation index ($\geq 3\%$ desaturation)
OHS	Obesity Hypoventilation Syndrome
OSA	Obstructive Sleep Apnea
PAP	Positive airway pressure

PS	Pressure Support
PSG	Polysomnography
PtCO2	Transcutaneous carbon dioxide
SIV	Site initiation visit
Standard ST mode	Commercially available ST modes utilizing a fixed EPAP
UAO	Upper airway obstruction
VAPS	Volume Assured Pressure Support

3. PROTOCOL SUMMARY

Objectives	The objective of this study is to evaluate AutoEPAP versus manual EPAP in iVAPS mode on the Astral device.
Study Design	This will be a prospective, multi-center, single-blind, randomized, cross-over design. The study will occur in a lab/hospital setting. Eligible subjects that represent patients with respiratory failure will complete two PSG study nights.
Number of Subjects	Up to 40 subjects overall will be randomized to obtain endpoint data on at least 36 evaluable subjects. This accounts for the expected dropout rate (10%).
Selection criteria	
Inclusion criteria for the study are:
 
 1. Participant has ability to provide written informed consent 2. Participants aged ≥ 18 years old 3. Participant has documented respiratory failure (e.g. sleep hypoventilation with historical PtCO₂ increase ≥ 10mmHg) and/or daytime hypercapnia (>45 mmHg) 4. Participant is currently using non-invasive positive pressure ventilation in ST or VAPS mode for ≥ 3 months 5. Participants with a previously documented AHI ≥ 5/hr 6. Participants with a recently (≤ 12 months ago) reviewed EPAP setting 
Exclusion criteria for the study are:
 
 1. Participants are not compliant on NIPPV (e.g. < 4 hr/night) 2. Participants who are pregnant 3. Participants on oxygen therapy ≥ 5 L/min 4. Participants with an invasive interface (e.g. tracheostomy) 5. Participants who have had an acute exacerbation within the last 3 months that resulted in a hospitalisation 6. Participants who are acutely ill, medically complicated or who are medically unstable 7. Participants in whom NIPPV therapy is otherwise medically contraindicated 8. Participants who have had surgery of the upper airway, nose, sinus, or middle ear within the previous 90 days 9. Participants with untreated, non-OSA sleep disorders, including but not limited to; insomnia, periodic limb movement syndrome, or restless legs syndrome. 10. Participants who have the following pre-existing conditions: severe bullous lung disease, recurrent pneumothorax or pneumomediastinum, cerebrospinal fluid leak, recent cranial surgery or trauma. 11. Participant does not comprehend English 12. Participant is unable or unwilling to provide written informed consent 13. Participant is physically and/or mentally unable to comply with the protocol 14. Participant is not suitable to participate in the trial for any other reason in the opinion of the investigator

Primary Endpoints	The primary outcome is the Oxygen Desaturation Index (ODI4%) as a measure of upper airway obstruction. The primary aim of this protocol is to compare ODI values following the use of the AutoEPAP algorithm in comparison to manual EPAP in VAPS mode.
Secondary Endpoints	
The secondary objectives will be used to determine if the AutoEPAP algorithm remains effective in treating respiratory failure patients.
 
 1. To assess the apnea hypopnea index (AHI) as measured by the Astral device. 2. To assess sleep-breathing parameters (e.g. nadir SpO₂ and PtCO₂) with AutoEPAP algorithm compared to manual EPAP on an Astral device. 3. To assess sleep parameters (e.g. sleep efficacy and arousal index) with AutoEPAP algorithm compared to manual EPAP on an Astral device.
Scheduled Visits	
Visit 1
 
 • Informed Consent • IEC requirements • Baseline Characteristics • Medical History 
Visit 2 (Night 1) and 3 (Night 2)
 
 • Mask fitting • Overnight PSG, including oximetry and PtCO₂

4. INTRODUCTION

4.1. Background Information

Patients with chronic respiratory insufficiency or failure such as those associated with Chronic Obstructive Pulmonary Disease (COPD) [1], Obesity Hypoventilation Syndrome (OHS) [2], Obstructive Sleep Apnea (OSA) [3] or Neuromuscular Disease (NMD) [4, 5] are increasingly managed with domiciliary non-invasive positive pressure ventilation (NIPPV) [1, 6-8].

Optimal settings of non-invasive ventilation are usually titrated manually and require time and expertise [9]. One such setting is expiratory positive airway pressure (EPAP) which is used to manage the lower airway and, if needed, prevent upper airway obstruction (UAO). In order to optimally adjust a fixed EPAP setting in a NIPPV device, a sleep study is usually required where respiratory flow waveforms may be monitored and recorded [10]. The waiting time for NIPPV titration sleep studies can be lengthy and/or be poorly performed due to resource limitations, and once they are, respiratory flow waveforms are often not recorded. In the instances where respiratory flow waveforms are recorded and analyzed, optimization of fixed EPAP settings are only based on the patient's condition for that single night. As a result, single night titrations may not capture significant alterations in factors which may affect the level of EPAP required, such as posture [11] and sleep state (e.g. supine in REM) [12].

Additionally, patient requirements may change over time due to progression of their chronic illness, weight fluctuations and prescribed medications, and, in some patients, changes in tissue edema location and severity with posture changes [13]. As such, the EPAP pressures, which are all under clinician control, are set during a titration study and must be high enough to deal with the worst conditions which may occur during the night. Clinicians must also regularly monitor patients, and possibly perform re-titrations to make sure the manually set EPAP is optimal.

For all these reasons, an automatic adjustable EPAP (i.e. "AutoEPAP") with clinician controlled minimum and maximum EPAP levels, may offer advantages over a fixed EPAP for managing UAO.

While an AutoEPAP algorithm could be used in the context of conventional fixed pressure support bilevel therapy (e.g. Spontaneous/Time (ST) mode), it would be useful to be used with a therapy mode which aims to automate all other aspects of ventilation as much as possible. Similar automated techniques have been successfully developed and established in current practice for OSA and periodic breathing [14, 15].

The Astral ventilator includes the Intelligent Volume Assured Pressure Support (iVAPS) (ResMed, Sydney, Australia, K152068) mode - a pressure support servoventilator which automatically adjusts pressure support to achieve a target alveolar ventilation (minute ventilation minus the anatomical deadspace) for patients who require mechanical continuous or intermittent ventilation. The amount of anatomical deadspace is calculated from an algorithm based on patient height. iVAPS also has a variable respiratory backup rate (i.e. Intelligent breathing rate; iBR), in which the set backup rate is delivered during periods of hypoventilation or central apnea only. When the user is breathing spontaneously and is triggering the device, the iBR algorithm will decrease the backup rate down to 2/3 of the 'target breath rate'. When necessary, iBR will rapidly increase the backup breath rate to the set 'target breath rate' to achieve target alveolar ventilation. The 'Target breath rate' is set according to the user's spontaneous breath rate during quiet wakefulness or in accordance with clinical needs (i.e. optimal PaO₂ and PaCO₂). The 'Target breath rate' can be measured and set by the ventilator itself, or manually adjusted by the clinician. Clinical trials evaluating a VAPS mode have been performed and have demonstrated VAPS is equivalent in treating respiratory insufficiency or failure as per manually titrated pressure support ventilation [16, 17, 19, 20, 21, 22, 23].

Patients with respiratory failure may also have upper airway obstruction. These patients therefore may benefit from NIPPV therapy which incorporates the management of volume assurance pressure support (i.e. VAPS) and UAO (i.e. AutoEPAP).

[figure not shown]
One such algorithm which has been developed is the iVAPS AutoEPAP algorithm (ResMed, Sydney, Australia). The iVAPS AutoEPAP algorithm has been previously trialed in patients with respiratory insufficiency or failure such as Obesity Hypoventilation Syndrome (OHS), Chronic Obstructive Pulmonary Disease (COPD) or neuromuscular disease (NMD) [24]. The patients completed two sleep studies (PSG) with iVAPS: one a manually titrated EPAP, and a second sleep study to observe and record the EPAP pressure generated from the AutoEPAP algorithm. Results showed that the algorithm was able to automatically titrate the EPAP level to effectively treat UAO in conjunction with respiratory insufficiency or failure compared to iVAPS mode with a fixed EPAP pressure. Treatment of UAO was shown to be comparable between the manually titrated EPAP with iVAPS, versus iVAPS AutoEPAP (mean AHI 1.7 (2.8) hr⁻¹ and 1.3 (2.3) hr⁻¹, respectively; p = 0.52) [24].

The aim of this study is to now compare the AutoEPAP algorithm with manual EPAP in iVAPS mode on an Astral ventilator. It is proposed that the automatic settings of AutoEPAP will be as effective at managing respiratory failure and UAO as manual EPAP on the Astral device. Specifically demonstrating that the AutoEPAP function is as effective at treating UAO as manual EPAP.

Astral is a homecare and hospital ventilator and not compatible with PSG systems for the measurement of respiratory flow estimate for the scoring of AHI. While total flow might be measured at the outlet of the Astral ventilator, this flow would include uncompensated components of flow from the mask vent and unintentional mask leak that will vary both within the breath due to varying pressure and over a longer time course due to changing mask leak. Based on the offset and variation of these components, accurate measurement of apneas and hypopneas would not be possible.

Since it is not technically feasible to calculate AHI, a surrogate for AHI is the ODI4% based on pulse oximetry that can be accurately obtained with PSG systems whilst a patient is using the Astral ventilator.

Clinically, ODI4% correlates exceptionally well with the AASM 2007 scoring rules for AHI (r = 0.98) [25]. See figure 1.

Figure 1. Correlation of ODI and AHI

Secondary aims include assessing the other potential physiological (i.e. sleep and sleep-breathing variables and gas exchange) that the algorithm may have on the patient.

4.2. Intended Use

The Astral device provides continuous or intermittent ventilatory support for patients who require mechanical continuous or intermittent ventilation (ResMed, Sydney, Australia, K152068).

Intelligent Volume Assured Pressure Support (iVAPS) is a mode of therapy for patients who require mechanical ventilation. The Astral device with the AutoEPAP algorithm and manual EPAP in iVAPS mode will be used in this protocol.

5. STUDY OBJECTIVES

5.1. Primary Objective

The primary outcome is the Oxygen Desaturation Index (ODI4%). The primary aim of this protocol is to compare ODI values following the use of the AutoEPAP algorithm in comparison to manual EPAP on the Astral ventilator.

5.2. Secondary Objectives

The secondary objectives will be used to determine if the AutoEPAP algorithm remains effective in treating respiratory failure.

1. To assess the apnea hypopnea index (AHI) as measured by the Astral device.
2. To assess sleep-breathing parameters (e.g. nadir SpO₂ and PtCO₂) with AutoEPAP algorithm compared to manual EPAP on an Astral device.
3. To assess sleep parameters (e.g. sleep efficacy and arousal index) with AutoEPAP algorithm compared to manual EPAP on an Astral device.

6. STUDY DESIGN

This will be a prospective, multi-center, single-blind, randomized, cross-over design. The study will occur in a lab/hospital setting. This study will be conducted at several centers in the United States.

6.1. Enrollment

Subjects will be recruited from pulmonary clinics at each site.

6.2. Selection of Subjects

6.2.1. Informed Consent

The consent form is written in accordance with applicable data privacy acts and FDA Regulations and approved by the responsible Institutional Review board (IRB).

The investigator or responsible staff will explain the nature, purpose and risks associated with the study. The patient will be given sufficient time to consider the study's implications before deciding whether to participate. Information materials created by the investigators and Sponsor must be approved by the responsible IRB prior to use.

A signed, IRB-approved consent form must be obtained from the patient prior to the performance of any protocol-related testing or treatment procedures. The consent process must be performed by a designated clinical study team member authorized by the IRB to consent patients and listed on the Delegation of Authority Log as having privileges to consent patients. A signed copy of the consent form must be maintained in the study files and a copy provided to the patient. The patient's permanent medical records should indicate study participation.

6.2.2. Study Population and Randomization

Enrolled subjects will be representative of patients with respiratory failure who fulfill the inclusion criteria and none of the exclusion criteria for this study and who sign the consent form(s) are considered as potential candidates for randomization into the study.

After verification of the subject's eligibility for the study, the study coordinator will assign the subject to 1 of 2 arms of the study, using the computer-generated randomization schedule provided by the Sponsor.

This is a single-blind study. This means that the subjects will be blinded to the randomization group that they are assigned to; the site Investigator and site study staff will know which randomization group the subject has been assigned to. The scorer(s) of the PSG will be blinded to which therapy is being used for objective determination of the primary and secondary endpoints.

6.2.3. Number of Subjects

Up to a total of 40 subjects will be enrolled across all centers.

6.2.4. Sample Size Justification

This study is powered for demonstrating ODI4% non-inferiority between the AutoEPAP algorithm and manual EPAP algorithm on the Astral device.

This protocol has been powered with the following inputs based on a previous study [26].

Expected mean difference in ODI: 0
 Expected standard deviation in ODI: 1.55
 Power = 80%
 Alpha = 0.05

Power to detect a difference of 1 per hour using a paired two-tailed t-test:

$$n = (Z\alpha + Z\beta)^2 \times (SD/difference)^2 = 22.84 = 23$$

Therefore, based on a crossover non-inferiority hypothesis test (one in which the outcome is dependent) we can be 95% sure that a sample size of 23 is sufficient to detect inferiority of AutoEPAP compared to with manual EPAP with respect to difference of ODI.

The update to this protocol (v3.0 to v4.0) was completed to be consistent with the recent FDA clearance of Astral with iVAPS. The increase in enrollment goal will provide additional power (95%) to detect a difference between AutoEPAP and manual EPAP.

We pre-specify a non-inferiority margin for ODI4% of 2 per hour (refer to Section 12). Basing the sample size on being able to detect the smallest difference in ODI (1 per hour) will provide greater power, through a larger sample size, in testing the non-inferiority margin (2 per hour).

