12. STATISTICAL ANALYSIS

Data recorded during 'Ramp' time (i.e. the time taken for the pressures to increase to the prescribed settings when the device is first turned on) will be excluded. Data will be checked for normality. If the data is normally distributed, descriptive data will be presented as mean and standard deviation (SD), and marginal differences. Comparisons between the two modes will be done using paired T-test.

If the data is not normally distributed, descriptive data will be presented as median and interquartile range (IQR). Comparative analysis between AutoEPAP and manual EPAP will be performed using the Mann-Whitney U test.

A $p < 0.05$ will be considered significantly different between AutoEPAP and manual EPAP if: 1. there is no significant difference between AutoEPAP and manual EPAP or 2. AutoEPAP is significantly better than manual EPAP, than the null hypothesis will be rejected and the AutoEPAP algorithm will be considered as 'passed'.

We pre-specify a non-inferiority margin for ODI4% of 2 per hour and specify a statistical test for non-inferiority as:

Non-inferiority margin for ODI: $d=2$

H0: $\mu_A - \mu_B \leq -d$ (new algorithm is inferior)

H1: $\mu_A - \mu_B > -d$ (new algorithm is non-inferior)

To show non-inferiority the lower bound of the 95th confidence interval of the difference between the groups must not cross the margin boundary (ODI4% of 2 per hour).

Which will be tested with a single-sided t-test with an alpha of 0.05 and a power of 80%. This pre-specified non-inferiority margin for ODI4% of 2 per hour is considered clinically unimportant, is the same margin as used in a previous study [26], and 2 per hour represents approximately 7% of severe UAO (30 per hour).

We also pre-specify that we will reject subjects where the ODI4% cannot be controlled during the control arm phase (manual EPAP). This is defined as an ODI ≥ 10 per hour. This process will be documented in the study Manual of Procedures and training provided for all participating sites.

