6.1. Statistical Analysis of the Primary Endpoint

The primary hypothesis will be tested using a one-sided paired t-test of the difference in ODI between Auto and Manual EPAP and compared to a non-inferiority margin for ODI4% of 2 events/hour. Additionally, the 95% upper one-sided confidence bound for the mean paired difference in ODI between manual and Auto EPAP will be calculated.

A cross-over analysis will be generated to investigate the influence of a possible period effect on the primary endpoint, paired change in ODI4% between Auto and Manual EPAP. Based on previous studies, ResMed does not expect the randomization order in which the subject used Auto versus Manual EPAP to affect the differences in ODI between the methods. A two-sample t-test comparing the two randomized treatment groups based on an alpha of 0.05 will be utilized for this analysis.

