Serious adverse events and events related to the Astral device will be tabulated for the Enrollment population, presenting the number of patients having one or more of each event and the associated percentage. A distinction will be made as to whether the subjects having adverse events were part of the ITT or Enrollment populations. In addition, a listing of these events will be presented, including the event description, time of occurrence, severity, outcome, action taken and relationship to the study device.

A separate listing of all other adverse events (non-serious and not related) occurring during the study period will be generated, including the event description, time of occurrence, severity, outcome, action taken and relationship to the study device.

9. Handling of Missing Values

The primary analysis will be based on the CC population. A multiple imputation sensitivity analysis will be done in the following way. Patients who dropout between the first and second PSG visit periods, will

have their second PSG visit data imputed, using the multiple imputation procedure MI in SAS. The imputation model will include randomization group and first period ODI4% as predictor variables. Results will be pooled using the MIANALYZE procedure in SAS.

10. Justification of Sample Size

Using a sample size calculation based on a normal distribution, the sample size required for 80% power to detect a difference in ODI of 1 event/hour, using a one-sided significance level of 0.05, was calculated to be 23 subjects assuming a SD of 1.55 in the Astral VAPS AutoEPAP Clinical Trial Protocol.

[Using the normal approximation formula for sample size as written in the protocol, I calculate a sample size of 15 patients required based on SD=1.55, beta=0.2, one-sided alpha=0.05, and a detection difference between groups of 1. Using a two-sided alpha of 0.05, the sample size is 19. Using PASS software (2) which uses the t distribution to calculate the sample size for paired means rather than the z distribution, the sample size is 17 for a one-sided alpha of 0.05, and 21 for a two-sided alpha of 0.05].

11. Protocol Deviations

Protocol deviations occurring during the study will be tabulated.

11. Statistical Software and Programming

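### The protocol's sample size of 23 does not follow from its stated inputs (19 two-sided, 15 one-sided), and the SAP shows this but leaves it uncorrected

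*Protocol*

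**What the plan says.** Protocol Section 6.2.4 lists an expected mean difference of 0, "Expected standard deviation in ODI: 1.55", power 80% and alpha 0.05. It describes the target as "Power to detect a difference of 1 per hour using a paired two-tailed t-test", gives n as (Zα + Zβ)² × (SD/difference)², and prints 22.84, rounded to 23. It then says that "we can be 95% sure that a sample size of 23 is sufficient to detect inferiority of AutoEPAP". The same section claims 95% power for the enlarged enrolment and sets a non-inferiority margin of 2 per hour. It explains that sizing on 1 per hour is meant to give more power at that margin.

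The Protocol Summary (Section 3) plans up to 40 randomized subjects "to obtain endpoint data on at least 36 evaluable subjects".

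Protocol Section 12 says of the non-inferiority test at 2 per hour: "Which will be tested with a single-sided t-test with an alpha of 0.05 and a power of 80" per cent. SAP Section 6.1 agrees on the direction: "The primary hypothesis will be tested using a one-sided paired t-test of the difference in ODI between Auto and Manual EPAP".

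SAP Section 10 restates the protocol's number for 80% power and 1 per hour as "using a one-sided significance level of 0.05, was calculated to be 23 subjects assuming a SD of 1.55". A bracketed note follows: "I calculate a sample size of 15 patients required based on SD=1.55, beta=0.2, one-sided alpha=0.05". The note adds 19 for two-sided alpha, and 17 (one-sided) or 21 (two-sided) from the t distribution. It neither replaces 23 nor explains the gap.

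**The concern.** There are three separate problems.

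- **Arithmetic.** The printed result does not come from the printed formula and inputs.
- **Sidedness.** The protocol calls the calculation two-tailed, the SAP attributes the same 23 to a one-sided level, and the primary test is one-sided. The number 23 matches neither description.
- **Attached power statements.** Being 95% sure is not a property of a calculation at 80% power. The 80% in Section 12 does not describe the 2 per hour test at 36 evaluable subjects, and neither document gives a power figure for that margin at that size.

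At stake is whether a reader or regulator can reproduce the sample-size justification. As it stands, the approved SAP contains a number and its own demonstration that the number is wrong.

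**Working it through.** **Inputs.** SD 1.55, difference 1 per hour, power 80%, alpha 0.05 (Protocol 6.2.4); margin 2 per hour, one-sided 0.05 (Protocol 12, SAP 6.1); 36 evaluable subjects (Protocol 3). Z for 80% power is 0.8416, and (1.55/1)² = 2.4025.

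**1. The printed formula, n = (Zα + Zβ)² × 2.4025**

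| Reading of alpha | Zα | n | Rounded up |
|---|---|---|---|
| Two-sided 0.05 | 1.960 | 18.86 | 19 |
| One-sided 0.05 | 1.645 | 14.85 | 15 |
| 0.0125 per tail | 2.2414 | 22.84 | 23 |

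With the other inputs as printed, only 0.0125 per tail gives 22.84. That is consistent with 0.05 having been halved twice, but the documents do not show what was done. To reach 22.84 at the stated alpha, the SD would have to be 1.71 (two-sided) or 1.92 (one-sided), or the power 86.9% or 92.5%.

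**2. The SAP's recalculation.** The normal formula gives 15 and 19, as above. The noncentral t distribution gives 17 one-sided and 21 two-sided. All four of the SAP's figures reproduce.

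**3. Power by the noncentral t distribution.** The noncentrality parameter is difference × √n / SD, with n − 1 degrees of freedom. For the 2 per hour margin the true difference is taken as 0.

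| n | 1/h, two-sided | 1/h, one-sided | 2/h margin, one-sided |
|---|---|---|---|
| 6 | – | – | 85% |
| 23 | 84.1% | 91.2% | >99.9% |
| 36 | 96.4% | 98.4% | >99.9% |

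For 95% power at 1 per hour the t-based n is 34 two-sided or 28 one-sided, so the protocol's 95% statement holds at 36. With a true difference of 0, power against 2 per hour at n = 36 falls to 80% when the SD of paired differences is 4.73, and 4.73/1.55 is about 3.

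**4. If 1.55 is a per-night SD.** This is an assumption; the within-subject correlation r is not given in the documents. The SD of differences is then 1.55 × √(2(1 − r)).

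| r | SD of differences | 1/h at n = 36, two-sided | 1/h at n = 36, one-sided | 2/h margin at n = 36 |
|---|---|---|---|---|
| 0 | 2.19 | 76% | 85% | >99.9% |
| 0.3 | 1.83 | 89% | 94% | >99.9% |
| 0.5 | 1.55 | 96% | 98% | >99.9% |

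On this reading the 95% statement holds from r of about 0.46 (two-sided) or 0.33 (one-sided). The printed formula, two-sided, would need 18.86 × 2(1 − r) subjects, which exceeds 23 when r is below about 0.39.

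**The case against.** The strongest reply is that 23 no longer governs the trial. The target is 36 evaluable of 40, the 95% power claimed for it is met, and the SAP already prints the correct values. The SAP can also be read as reporting the protocol's number and then disputing it. All of this limits the consequence, and it is why the point is one of traceability. It does not remove the error: the protocol still carries a result that its formula does not give, and the SAP assigns to it a sidedness that the protocol does not state.

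A second reply is that 23 is close to the t-based 21, or to 19 inflated for 10% dropout (19/0.9 = 21.1, so 22). The printed formula uses normal quantiles and has no dropout term, and neither route gives 22.84.

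A third is that sizing on 1 per hour while testing against 2 was deliberate. That is fair: Section 6.2.4 says so, and the choice is not criticized here. The 80% in Section 12 may likewise be the design power carried over, but there it is attached to the 2 per hour test, which it does not describe.

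The last is that calling the error conservative depends on what 1.55 represents. In part this stands. The slip raises n above what the formula gives, whatever the SD means. Whether 23 would have been enough, and whether the 95% statement holds at 36, does depend on the SD. The paired formula and the SAP's paired-means calculation favour the SD of differences, but the protocol's wording does not settle it.

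**Conclusion.** The concern holds. The stated 23 is 4 above the two-sided result of its own formula and 8 above the one-sided result (2 and 6 above by the t distribution). The two documents also disagree on its sidedness. The arithmetic error is in the safe direction and changes neither enrolment, margin, test nor primary conclusion. If 1.55 is the SD of paired differences, the planned 36 evaluable subjects support the 95% power claim for 1 per hour and give well over 99.9% power for non-inferiority at 2 per hour with a true difference of 0. If it is a per-night SD, the 95% claim depends on an unstated correlation, while power at the 2 per hour margin stays above 99.9%.

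**What to change.** In both documents, replace 23 by the value for one stated alpha, preferably that of the primary test:

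> n = (1.645 + 0.842)² × (1.55/1)² = 14.85, i.e. 15 (17 by the t distribution), one-sided alpha 0.05, 80% power for 1 per hour.

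If two-sided alpha is kept for the 1 per hour difference, use 19 (21 by t) in both documents. Delete the claim of being 95% sure. Replace the 80% in Protocol Section 12 and the open note in SAP Section 10 by a dated, recorded correction that keeps the four recalculated values and adds:

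> With 36 evaluable subjects, power is 98.4% (one-sided 0.05) or 96.4% (two-sided 0.05) for 1 per hour, and above 99.9% for non-inferiority at 2 per hour with true difference 0, if 1.55 is the SD of paired differences.

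The sponsor should confirm from its own source report (protocol reference 26) whether 1.55 is that SD, and check which input produced 22.84. If 1.55 is a per-night SD, show the range over the correlation instead. The cost is wording, a recorded correction in both documents and one look-up. Enrolment, test and margin do not change.
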